10.1 Analysis sets

10.1.1 Full Analysis Set

Parts 1 & 2: Safety run-in and biomarker cohort

For each part, the full analysis set (FAS) and safety set are defined in the same way and comprise all subjects to whom study treatment has been assigned and who received at least one dose of any study treatment (i.e. at least one dose of any component of PDR001 (including incomplete infusion), dabrafenib, or trametinib). Subjects will be analyzed according to the study treatment they have been assigned to.

Part 3: Double-blind, randomized, placebo-controlled part

The FAS comprises all subjects to whom study treatment has been assigned by randomization, regardless of whether or not treatment was administered. According to the intent to treat principle, subjects will be analyzed according to the treatment and strata they have been assigned to during the randomization procedure. This population will be the primary population for efficacy analyses.

10.1.2 Safety set

Parts 1 & 2: Safety run-in and biomarker cohort

See definition of FAS.

Part 3: Double-blind, randomized, placebo-controlled part

The Safety Set includes all subjects who received at least one dose of study treatment (i.e. at least one dose of any component of PDR001 or placebo (including incomplete infusion), dabrafenib, or trametinib). Subjects will be analyzed according to the study treatment received, where treatment received is defined as the randomized treatment if the subject took at least one

dose of that treatment or the first treatment received if the randomized treatment was never received.

10.1.3 Per-Protocol set

Parts 1 & 2: Safety run-in and biomarker cohort

Not applicable.

Part 3: Double-blind, randomized, placebo-controlled part

The Per-Protocol Set (PPS) will only be used for sensitivity analyses on the primary variables. The PPS consists of a subset of the subjects in the FAS who are compliant with requirements of the clinical study protocol (CSP).

Oncology standards for protocol deviations **potentially** leading to exclusion from the PPS are:

- type of indication different from those required by the CSP (e.g., incorrect histology/cytology, not refractory, not metastatic, different grade of cancer, etc.)
- if prior therapy does not match with CSP requirements in terms of number and types of previous therapy regimens
- missing or incomplete documentation of stage of disease (as required in the CSP)
- if ECOG performance status at least 2 categories worse than protocol-defined inclusion criteria
- another anti-neoplastic therapy administered after start of study treatment and prior to first tumor assessment
- study treatment received different from treatment assigned by randomization

Full specifications of deviations leading to exclusion will be described in the Study Specific Document (SSD) document.

10.1.4 Dose-determining analysis set

Part 1: Safety run-in

The Dose-Determining Set (DDS) includes all subjects who received at least one dose of study treatment who either 1) met the minimum exposure criterion and had sufficient safety evaluations, or 2) experienced a DLT during the first 8 weeks (56 days) of PDR001 in combination with dabrafenib and trametinib dosing.

A subject meets the minimum exposure criterion if the subject receives at least 1 dose of PDR001, and takes at least 50% of the planned cumulative doses of dabrafenib and trametinib within the first 8 weeks (56 days) of treatment. Subjects who do not experience a DLT during the first 8 weeks are considered to have sufficient safety evaluations if they have been observed for at least 8 weeks following the first dose of PDR001 in combination with dabrafenib and trametinib, and are considered by both the Sponsor and Investigators to have enough safety data to conclude that a DLT did not occur. Patients who do not meet the minimum exposure criterion due to an AE will be counted as having a DLT. Patients who do not meet the minimum exposure criterion for reasons other than AE's (e.g., rapid disease progression or non-compliance) will

not be included in the DDS. **Parts 2 & 3: Biomarker cohort and double-blind, randomized, placebo-controlled part**

Not applicable.

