7.1.4.1 Replacement policy

Part 1: Safety run-in

If a subject is considered as non-evaluable for the Dose-Determining Set (DDS), a new subject will be enrolled until at least the minimum number of 6 evaluable subjects is achieved within the cohort.

Part 2: Biomarker cohort

If not possible to collect at least three tumor biopsies (at screening, C1D15 and one additional biopsy on treatment), a new subject will be enrolled to allow for a sufficient number of evaluable subjects for the biomarker studies.

Part 3: Double-blind, randomized, placebo-controlled part

Subjects will not be replaced.

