10.4.1 Variables

Part 1: Safety run-in

The primary variable is the incidence of DLTs during the first 8 weeks (56 days) of treatment for each dose level associated with administration of PDR001 in combination of dabrafenib and trametinib.

Part 2: Biomarker cohort

The primary variable is PD-L1 levels and CD8+ cells and changes from baseline.

Part 3: Double-blind, randomized, placebo-controlled part

The primary efficacy variable is PFS, defined as the time from the date of randomization to the date of the first documented progression per RECIST 1.1 or death due to any cause. PFS will be assessed via local review according to RECIST 1.1 (see [Appendix 1](#) for further details). Censoring conventions are provided below in [Section 10.4.3](#).

Local scans will be sent to a blinded, independent central reviewer who will provide assessments using both RECIST 1.1 and tumor response criteria based on guidelines for immunotherapy, and these centrally reviewed data will be used for sensitivity analysis.

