10.8 Sample size calculation

Part 1: Safety run-in

No formal statistical power calculations to determine sample size were performed for this part of the study. In the case that the starting dose (PDR001 400 mg i.v. every 4 weeks with the fixed dose combination of 150 mg BID dabrafenib and 2 mg QD trametinib) is confirmed to be safe and tolerated, the safety run-in part is expected to enroll 6 evaluable subjects (i.e. who met the minimum exposure criterion and had sufficient safety evaluations during the first 8 weeks of PDR001 in combination with dabrafenib and trametinib dosing). Otherwise, up to 18 additional subjects are foreseen to be enrolled to assess additional cohorts.

Part 2: Biomarker cohort

No formal statistical power calculations to determine sample size were performed for this part of the study. Approximately 20 evaluable subjects (i.e. who have at least one tumor biopsy at screening and at least two during triple combination therapy) will be enrolled in this cohort.

[figure not shown]
Part 3: Double-blind, randomized, placebo-controlled part

The sample size calculation is based on the primary variable PFS. The hypotheses to be tested and details of the testing strategy are described in [Section 10.4.2](#).

Based on data from two pivotal randomized Phase III studies (MEK115306 [COMBI-d]) and MEK116513 [COMBI-v]), the median PFS time in the control arm is expected to be 11 months. Ignoring delayed treatment effect, it would be expected that the experimental treatment response would result in a hazard ratio of 0.60 (which corresponds to an increase in median PFS to 18.33 months under the exponential model assumption). Given knowledge of a potential delayed treatment effect, it is hypothesized that there will be no difference between treatment arms until 5 months after the start of treatment for PFS. Therefore, it is assumed that the HR between the groups will be equal to 1 for the first 5 months. Thereafter, exponential survival distributions are assumed, with an HR of 0.60. This will result in an overall HR=0.739 ([Kalbfleisch 1981](#)) at the time of the final PFS analysis (given the assumed 5 month delayed treatment effect, this equates to median PFS times of 15.0 and 11 months in the PDR001 in combination with dabrafenib and trametinib combination arm and the dabrafenib and trametinib plus placebo group, respectively).

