14.2.2 Statistical model

For each of the k dosing regimens ($k = 1, 2, 3$), a separate statistical model will comprise of single-agent toxicity parts and interaction parts to describe both two-way and three-way drug safety interactions.

- Model 1 will incorporate DLT data from the first 8 weeks of triple combination treatment in cohort 1 (400 mg i.v. PDR001 Q4W + 150 mg BID dabrafenib + 2 mg QD trametinib)
- Model 2 will incorporate DLT data from the first 8 weeks of triple combination treatment in cohort -1a (400 mg i.v. PDR001 Q8W + 150 mg BID dabrafenib + 2 mg QD trametinib)
- Model 3 will incorporate DLT data from the first 8 weeks of triple combination treatment in cohort -1b (4 weeks run-in of 150 mg BID dabrafenib + 2 mg QD trametinib, followed by 400 mg i.v. PDR001 Q4W + 150 mg BID dabrafenib + 2 mg QD trametinib)

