14.2.3.2 Prior distribution for interaction parameters

Based on the available information, there is a possibility of an antagonistic or synergistic interaction between dabrafenib and trametinib that will be taken into account for model 1 (dosing regimen 1) and model 2 (dosing regimen -1a). For model 3 (dosing regimen -1b), the interaction is centered at a 0% increase in odds of DLT, given that DLT's for the triple combination in this dosing regimen will be assessed after a 4 week run-in with dabrafenib and trametinib. No interaction is expected for the other two-way combinations, and for the three-way combination no interaction is expected over and above what is already described. However, in all cases, considerable uncertainty remains as to the true interaction, and normal

priors are used that allow for both synergistic and antagonistic toxicity. The following assumptions will be used for interaction parameters for model k ($k = 1, 2, 3$).

Dabrafenib and trametinib for model 1 (dosing regimen 1) and 2 (dosing regimen -1a):

- η_{12k} is normally distributed and centered at 1.2, i.e. a 20% increase in odds of DLT over independence at the combination starting dose
- 97.5th percentile is $\log(3)$, i.e. a 3-fold increase in odds of DLT over independence at the combination starting dose

Dabrafenib and trametinib for model 3 (dosing regimen -1b):

- η_{123} is normally distributed and centered at 0, i.e. a 0% increase in odds of DLT over independence at the combination starting dose
- 97.5th percentile is $\log(2)$, i.e. a 2-fold increase in odds of DLT over independence at the combination starting dose

Dabrafenib and PDR001 for all 3 models:

- η_{13k} is normally distributed and centered at 0, i.e. a 0% increase in odds of DLT over independence at the combination starting dose
- 97.5th percentile is $\log(2)$, i.e. a 2-fold increase in odds of DLT over independence at the combination starting dose

Trametinib and PDR001 for all 3 models:

- η_{23k} is normally distributed and centered at 0, i.e. a 0% increase in odds of DLT over independence at the combination starting dose
- 97.5th percentile is $\log(2)$, i.e. a 2-fold increase in odds of DLT over independence at the combination starting dose

Dabrafenib, trametinib and PDR001 for all 3 models:

- η_{123k} is normally distributed and centered at 0, i.e. a 0% increase in odds of DLT over independence at the combination starting dose

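### For DL-1b, the minimum exposure criterion and the AE-to-DLT rule in 10.1.4 are not tied to the first PDR001 dose and contradict the triple-combination DLT window

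*Protocol*

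**What the plan says.** Section 7.1.3 starts study treatment on C1D1. Table 7-1 starts PDR001 in DL-1b at C2D1, so days 1 to 28 are dabrafenib and trametinib only.

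Section 10.1.4 defines minimum exposure in two parts, both of which must be met. The PDR001 part is met "if the subject receives at least 1 dose of PDR001". The second part concerns the partner drugs and requires that the subject "takes at least 50% of the planned cumulative doses of dabrafenib and trametinib within the first 8 weeks (56 days) of treatment". It then rules: "Patients who do not meet the minimum exposure criterion due to an AE will be counted as having a DLT". Subjects who miss the criterion for other reasons leave the dose-determining set (DDS). No run-in exception is given.

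In the same section, entry to the DDS by DLT, and the observation period for a subject without a DLT, both run over 8 weeks of PDR001 given with dabrafenib and trametinib. Sections 10.4.2, 10.4.3 and 10.8 use that window too. Section 14.2.2 says: "Model 3 will incorporate DLT data from the first 8 weeks of triple combination treatment in cohort -1b". Section 14.2.3.2 says: "DLT's for the triple combination in this dosing regimen will be assessed after a 4 week run-in with dabrafenib and trametinib".

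Section 10.4.1 reads: "The primary variable is the incidence of DLTs during the first 8 weeks (56 days) of treatment for each dose level". The sentence goes on to refer to administration of the three-drug combination, so it can be read either way.

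For Part 2, 7.1.4.1 replaces a subject as follows: "If not possible to collect at least three tumor biopsies (at screening, C1D15 and one additional biopsy on treatment". Section 10.8 instead defines evaluable subjects as those "who have at least one tumor biopsy at screening and at least two during triple combination therapy".

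**The concern.** For DL1 and DL-1a, PDR001 starts on C1D1, so treatment time and triple-combination time coincide. For DL-1b they differ by 28 days, and 10.1.4 uses both clocks without saying so.

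The purpose of Part 1 is to choose the Part 3 regimen from the DLT risk of the triple combination. With about six evaluable subjects per cohort, one misassigned subject can matter. The two effects run in opposite directions. Counting a run-in stop as a DLT overstates triple-combination risk. Admitting a subject who had almost no partner drug alongside PDR001 understates it. DL-1b data also enter Model 2 with weight 0.571, so an error there carries into the assessment of DL-1a.

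**Working it through.** **1. The two windows for DL-1b.** Days 1 to 56 of treatment consist of run-in days 1 to 28 and triple-combination days 29 to 56. The first 8 weeks of the triple combination are days 29 to 84. The overlap is 28 days, and no partner-drug exposure is required for days 57 to 84.

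**2. AE stop in the run-in.** The subject has had no PDR001, so minimum exposure fails, and the cause is an AE. The first route into the DDS (exposure plus sufficient observation) is closed. The second route (a DLT during triple dosing) is also closed, because there was no triple dosing. The AE sentence nevertheless counts the subject as a DLT. One section gives two answers for the same person.

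**3. Partner-drug share of a full run-in.** Dabrafenib: 28 × 2 = 56 of 112 doses. Trametinib: 28 of 56 doses. Both are exactly 50%, which meets a threshold of at least 50%. On a clock that starts at the first PDR001 dose, the same run-in dosing contributes 0%.

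**4. Reproducing the plan's model.** Weight = 1/(1 + 2·n·τ²/sd²), bracketed as in 14.2.3.3.
- Model 3 (n = 6, τ = 1, sd = 2): 1/(1 + 12/4) = 0.25, as stated.
- Model 2 (τ = 0.5): 1/(1 + 3/4) = 0.571, as stated.

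Model 3 was re-run by importance sampling (1.5 million draws) from the Table 14-18 priors with the Table 14-13 data at their stated weights. Prior probability of excessive toxicity: 0.105, against 0.102 in Table 14-19. Prior median: 0.134, against 0.132.

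**5. Effect of one extra DLT in -1b under Model 3**, with 3/6 DLTs in regimen 1 and the limit at 25%:

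| DLTs in -1a | -1b at 2/6: re-run (Table 14-21) | -1b at 3/6: re-run (Table 14-21) |
|---|---|---|
| 0 | 0.173 (0.175) | 0.380 (Stop) |
| 1 | 0.202 (0.198) | 0.422 (Stop) |
| 2 | 0.234 (0.236) | 0.466 (Stop) |

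**6. All one-DLT steps in -1b in Table 14-21**, by scenario number:

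| DLTs in -1a | 0 to 1 | 1 to 2 | 2 to 3 |
|---|---|---|---|
| 0 | 1→2 no change | 2→5 no change | 5→10 -1b stops |
| 1 | 3→4 no change | 4→7 no change | 7→12 -1b stops |
| 2 | 6→8 no change | 8→9 no change | 9→14 -1b stops |
| 3 | 11→13 no change | 13→15 both stop | 15→16 already stopped |

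Four of the 12 steps change the recommendation. In 13→15, both regimens were open (0.190 for -1a, 0.107 for -1b) and both close. In 9→14, the value for -1a also rises from 0.139 to 0.215, which shows the carry-over through the 0.571 weight. These comparisons hold the cohort at six, so they assume that the misassigned subject would otherwise have been replaced by one without a DLT.

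**7. Part 2 under DL-1b.** The C1D15 biopsy precedes any PDR001. A subject with screening, C1D15 and Cycle 4 biopsies satisfies 7.1.4.1, but has one biopsy on triple therapy where 10.8 asks for two. Under DL1 and DL-1a the two rules agree.

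**The case against.** A reader might infer that the protocol treats the run-in as triple-combination time throughout. It does not: the DLT window, the observation window and Model 3 all run on the combination, and the quoted part of 10.4.1 is followed by a combination qualifier. Nor does run-in dosing alone satisfy minimum exposure, because at least one PDR001 dose is needed. Nor does all run-in toxicity become a DLT: under 10.1.4 only an AE that causes exposure failure does, and an AE that resolves and lets PDR001 start does not.

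The second effect is partly guarded. A subject without a DLT must be observed for 8 weeks after the first combination dose, and both sponsor and investigators must judge the data sufficient. Reaching 50% from the run-in alone also needs perfect compliance. That guard stands, but it is a case-by-case judgement and does not repair the criterion.

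It can also be argued that the run-in belongs to regimen -1b, so counting an AE that prevents PDR001 is a cautious measure of the whole regimen. That is a legitimate target, but not the one modelled. Section 14.2.3.2 centres the dabrafenib-trametinib interaction at 0 for Model 3, against 0.182 for Models 1 and 2, precisely because its DLTs are assessed after the run-in. Run-in events would therefore be set against a prior that does not describe them.

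Section 6.2, with the dosing-decision rules, is in the part not shown and may hold a DL-1b provision. If so, 10.1.4 still needs to agree with it. For Part 2, 10.4.2 summarises results by visit, so a doublet-only C1D15 change need not be read as an effect of PDR001. The Cycle 4, progression and optional biopsies could also supply two on triple therapy.

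**Conclusion.** The point holds as an internal contradiction confined to DL-1b. Followed literally, 10.1.4 counts an AE stop before any PDR001 as a triple-combination DLT and lets run-in doses fill the whole partner-drug half of minimum exposure.

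The consequence is conditional. One such count changes the recommendation in 4 of the 12 one-DLT steps illustrated, all of which assume 3/6 DLTs in regimen 1. It leaves the recommendation unchanged in the other eight.

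The frequency is unknown. It is tempting to borrow the doublet rates in Table 14-13 (23/209 = 11.0% and 51/350 = 14.6%), but those count patients meeting DLT criteria over 8 weeks, not patients leaving within 4 weeks before PDR001.

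DL-1b opens only if regimen 1 is not tolerated. This version also postdates the final PFS analysis, so what remains is chiefly a consistent DDS definition for reporting, and only if DL-1b was used. The Part 2 mismatch is real but secondary.

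**What to change.** Reconcile 10.1.4 and 10.4.1 with Appendix 2 and with Section 6.2. For the DL-1b analysis set:

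- Run the 50% partner-drug criterion over the 8 weeks from the first PDR001 dose, the same window as the DLT assessment, and state that window in 10.4.1.
- Classify subjects who leave before the first PDR001 dose as non-evaluable for the DDS, and replace them under 7.1.4.1.
- Limit the AE-to-DLT sentence to subjects who have started PDR001.
- Report run-in AE discontinuations separately, with the number who entered the run-in as denominator, so that tolerability of the whole regimen stays visible.

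For Part 2 under DL-1b, adopt one evaluability rule across 7.1.4.1 and 10.8, and label the C1D15 biopsy as taken on dabrafenib and trametinib only.

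The cost is wording, possibly one or two more DL-1b subjects, and a DLT rate that is conditional on completing the run-in. The separate run-in report is there to offset that last limitation. The change concerns analysis-set definitions only and alters no dose or dosing rule.

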10.1.5 Pharmacokinetic analysis set

The following analysis sets will be derived separately for each of the 3 parts. The PDR001 pharmacokinetic analysis set (PAS-PDR001) includes all subjects who provide at least one evaluable PDR001 PK concentration. For a concentration to be evaluable, subjects are required to:

- Received one of the planned treatments of PDR001 prior to sampling
- For pre-dose samples, have the samples collected before the next dose administration
- For end-of-infusion samples, have the samples collected within 2 hours post infusion

The dabrafenib and trametinib Pharmacokinetic analysis set (PAS-D+T) includes all subjects who provide at least one evaluable dabrafenib or trametinib PK concentration. For a concentration to be evaluable, subjects are required to:

- Receive a dose of dabrafenib and trametinib prior to sampling
- For pre-dose samples, have the samples collected before the next dose administration
- For post-dose samples, do not vomit within 4 hours after the dosing of dabrafenib and trametinib

10.1.6 Other analysis sets

The *Immunogenicity prevalence set* includes all subjects in the FAS with a determinant baseline IG sample **or** at least one determinant post-baseline IG sample.

The *Immunogenicity incidence set* includes all subjects in the Immunogenicity prevalence set with a determinant baseline IG sample **and** at least one determinant post-baseline IG sample.

Additional details, including definition of determinant, will be provided in the SAP.

10.1.6.1 Efficacy/evaluable set

Not applicable.

[figure not shown]
10.2 Subject demographics/other baseline characteristics

Parts 1 & 2: Safety run-in and biomarker cohort

Demographic and other baseline data including disease characteristics will be listed and summarized descriptively by dose cohort for the FAS. Relevant medical histories and current medical condition at baseline will be summarized separately by system organ class and preferred term, by dose cohort.

Part 3: Double-blind, randomized, placebo-controlled part

Demographic and other baseline data including disease characteristics will be listed and summarized descriptively by treatment group and for all subjects for the FAS and safety set.

Relevant medical histories and current medical at baseline will be summarized separately by system organ class and preferred term, by treatment group and for all subjects.

10.3 Treatments (study treatment, concomitant therapies, compliance)

The safety set will be used to summarize treatment data. Categorical data will be summarized as frequencies and percentages. For continuous data, mean, standard deviation, median, 25th and 75th percentiles, minimum, and maximum will be presented.

Parts 1 & 2: Safety run-in and biomarker cohort

The duration of exposure to PDR001, dabrafenib, and trametinib as well as the dose intensity (computed as the ratio of actual cumulative dose received and actual duration of exposure) and the relative dose intensity (computed as the ratio of dose intensity and planned dose intensity) will be summarized by means of descriptive statistics using the safety set. The duration of exposure will also be presented for the study treatment by arm.

The number of subjects with dose adjustments (reductions, interruption, or permanent discontinuation) and the reasons will be summarized by dose cohort, and all dosing data will be listed.

Concomitant medications and significant non-drug therapies prior to and after the start of the study treatment will be listed and summarized according to the Anatomical Therapeutic Chemical (ATC) classification system, by dose cohort.

Part 3: Double-blind, randomized, placebo-controlled part

The duration of exposure to PDR001 (or matching placebo), dabrafenib, and trametinib as well as the dose intensity (computed as the ratio of actual cumulative dose received and actual duration of exposure) and the relative dose intensity (computed as the ratio of dose intensity and planned dose intensity) will be summarized by means of descriptive statistics using the safety set. The duration of exposure will also be presented for the study treatment by arm.

The number of subjects with dose adjustments (reductions, interruption, or permanent discontinuation) and the reasons will be summarized by treatment group and for all subjects, and all dosing data will be listed.

Concomitant medications and significant non-drug therapies prior to and after the start of the study treatment will be listed and summarized according to the ATC classification system, by treatment group and for all subjects.

[figure not shown]
